3.6.4 Administration of other anti-cancer agents

Subjects must not receive any other concurrent anti-cancer therapy, including investigational agents, while on study treatment. Subjects may continue the use of bisphosphonates for bone disease and corticosteroids for the symptomatic control of brain metastases, provided the dose is stable in the last 7 days and does not exceed 10mg of prednisolone or equivalent.

Full details of all of these treatments are recorded in the subject's notes and appropriate section of the eCRF.

3.6.5 Blood donation

Subjects should not donate blood while participating in this study or for at least 90 days following the last infusion of durvalumab, or until at least 3 days after the last administration of olaparib.

3.6.6 Other concomitant treatment and medications

1. No other chemotherapy specified outside of this protocol, hormonal therapy (hormone replacement therapy [HRT] is acceptable), or other novel agent is to be permitted during the course of the study for any subject (the subject can receive a stable low dose of corticosteroids during the study, as per exclusion criteria above).
2. Live virus and bacterial vaccines should not be administered while the subject is receiving study medication and during the 30-day follow-up period. An increased risk of infection resulting from administration of live virus and bacterial vaccines has been observed with conventional chemotherapy drugs; the effects with olaparib are unknown.
3. Subjects should avoid concomitant use of drugs, herbal supplements, and/or ingestion of foods known to modulate CYP3A4 enzyme activity from the time they enter the screening period until 30 days after the last dose of study medication. *In vitro* data have shown that the principal enzyme responsible for the formation of the 3 main metabolites of olaparib is CYP3A4, and consequently, this restriction is required to ensure subject safety.
4. Concomitant use of strong CYP3A inhibitors (eg, itraconazole, telithromycin, clarithromycin, ketoconazole, voriconazole, nefazodone, posaconazole, ritonavir,

lopinavir/ritonavir, indinavir, saquinavir, nelfinavir, boceprevir, telaprevir) and moderate CYP3A inhibitors (e.g., amprenavir, aprepitant, atazanavir, ciprofloxacin, crizotinib, darunavir/ritonavir, diltiazem, erythromycin, fluconazole. Fosamprenavir, imatinib, verapamil) is not allowed.

5. Concomitant use of strong CYP3A inducers (eg, phenytoin, rifampicin, carbamazepine, St. John's Wort) and moderate CYP3A inducers (eg, bosentan, efavirenz, etravirine, modafinil, nafcillin) is not allowed.
6. Immunosuppressive medications should not be given concomitantly or given as a premedication prior to infusion. This includes but is not limited to systemic corticosteroids at doses not exceeding 10 mg/day of prednisone or equivalent, methotrexate, azathioprine, and tumor necrosis factor-alpha (TNF- α) blockers.

The following are allowed exceptions:

- Use of immunosuppressive medications for the management of durvalumab-related AEs,
 - Short-term steroid premedication for patients receiving durvalumab if required for documented hypersensitivity reactions.
 - Use in patients with contrast allergies as a premedication/prep prior to scans.
 - In addition, use of inhaled, topical, and intranasal corticosteroids is permitted.
7. Subjects who are taking warfarin may participate in this study; however, it is recommended that prothrombin time (INR and APTT) be monitored carefully at least once per week for the first month, then monthly if the INR is stable. Subcutaneous heparin is permitted. The reason(s) for the use, doses, and dates of treatment should be recorded in the subject's medical records and appropriate section of the eCRF.
 8. All medications (prescriptions or over-the-counter medications) continued at the start of the trial or started during the study or until 30 days from the end of the last protocol treatment and that are different from the study medication must be documented.

3.7 Data Management

Data Management will be performed by Duke Clinical Research Institute (DCRI). DCRI is responsible for the development of a 21 CFR Part 11-compliant electronic data management system. This system will include eCRF screens, automated data validation checks and a randomization module. The data validation checks include checks for out-of-range and logically inconsistent data.

The DCRI will be responsible for medical coding. Adverse events will be coded using DCRI's current version of the medical dictionary for regulatory activities (MedDRA) updated semi-annually. The concomitant medications will be coded using DCRI's current version of the World Health Organization Drug Dictionary Enhanced (WHO DDE) updated semi-annually.

Protocol specific data management activities will be defined in the Data Management Plan. Quality control procedures will be applied to each stage of data handling to ensure that all data are reliable and have been processed correctly.

When all data have been coded, validated and locked, a clean file will be declared.

3.8 Evaluation and calculation of variables

The primary efficacy outcome measure is as follows:

- PFS (progression free survival) defined as the time from randomization to the first occurrence of disease progression (as determined using RECIST 1.1 criteria and assessed by the Investigator) or death from any cause on study. Death on study is defined as death from any cause within 30 days of the last dose of study treatment regimen. Tumor progression will be assessed locally at each site by the investigators according to RECIST 1.1. No independent review of tumor progression is planned. PFS with disease progression determined by iRECIST for patients on the combination arm will also be examined in exploratory data analysis.

The secondary efficacy outcome measures in all subjects are as follows:

- OS (overall survival) defined as the time from entry onto trial until death from any cause.
- ORR (overall response rate) defined as the subjects achieving Complete Response or Partial Response as defined by RECIST 1.1.
- CBR (clinical benefit rate) defined as subjects achieving Complete Response, Partial Response or Stable disease \geq 24 weeks

3.9 Calculation or derivation of efficacy variable(s)

The following definitions and criteria (from RECIST 1.1) should be used for the baseline evaluations of existing disease, and for the ongoing evaluation of tumor responses. All measurements should be taken and recorded in metric notation, using a ruler or callipers. For the case of skin lesions, documentation (jpg file, preferred) by color photography, and a measurement with a ruler to estimate the size of the lesion, is recommended.

- **Measurable disease** - the presence of at least one measurable lesion.
- **Measurable lesions** - lesions that can be accurately measured in at least one dimension with longest diameter (LD) 20 mm using conventional techniques or 10 mm with spiral CT scan. Lymph nodes must be 15mm or greater (by spiral CT) in the shortest diameter to be considered measurable.

- **Non-measurable lesions** - all other lesions, including small lesions (LD <20 mm with conventional techniques or <10 mm, Lymph nodes <15mm SD with spiral CT scan), ie, bone lesions, ascites, pleural/pericardial effusion, cystic lesions, and also abdominal masses that are not confirmed and followed by imaging techniques.

Conventional CT should be performed with cuts of 10 mm or less in slice thickness contiguously. Spiral CT should be performed using a 5-mm contiguous reconstruction algorithm.

All imaging methods should be performed according to institutional standards with each subject having consistency of methods beginning from baseline through the course of the study.

3.9.1 Evaluation of Best Overall Response

The best overall response is the best response recorded from the start of the treatment until disease progression and is determined as per Tables 10 and 11.

To be considered a response, CR or PR must persist for a minimum of 4 weeks. If, at the time of tumor response evaluation, either a PR or CR is observed, the same radiographic study should be repeated four weeks later for confirmation of response. After this confirmatory study, subjects should return to the schedule of evaluations as previously described.

4 STUDY PROCEDURES AND ASSESSMENTS

The schedule of assessments is provided in Appendix A. Descriptions of the scheduled evaluations are outlined below and complete information on study drugs and dosing is provided.

Before study entry, throughout the study, and at the follow-up evaluation, various clinical and diagnostic laboratory evaluations are outlined. The purpose of obtaining these detailed measurements is to ensure adequate safety and tolerability assessments. Clinical evaluations and laboratory studies may be repeated more frequently if clinically indicated. This study will use local site labs for laboratory testing and for safety laboratory evaluations; biomarker specimens collected will be stored at study sites until end of study then shipped to the Duke Pathology central biorepository for future research.

4.1 Subject enrollment and randomization

4.1.1 Informed consent

Investigators must ensure that subjects are clearly and fully informed about the purpose, potential risks, and other critical issues regarding this clinical study for which they are volunteering to participate.

Before any study procedures are performed, potential subjects will have the outline of the study described to them, and they will be given a written informed consent document to read. If they consent to participate in the study, they will indicate that consent by signing and dating the informed consent document in the presence of study personnel. Any subject who signs the

consent form will be considered a “screened” subject.

4.1.2 Screening Procedures

After written informed consent is obtained according to ICH GCP and local regulations, the subject’s eligibility for the study and baseline disease status will be evaluated. This will occur in a screening visit during which the following will be evaluated and documented within 14 days prior to first dose of study drug(s).

Investigations, such as CT or MRI scans that have been performed as part of routine clinical practice, can be used as part of the screening process if performed within 28 days of first dose of study treatment; however, no non-standard of care investigations or tests that are study specific and required for screening may be performed prior to signature of the informed consent form.

The following baseline information should be obtained within 28 days prior to randomization:

- Demographic data and medical history, including previous and current diseases and medications, and confirmation of all prior treatments for metastatic breast cancer, including platinum based treatment requirements of investigator choice.
- Check availability of archival tumor tissue sample or new tumor biopsy if archival tissue unavailable
- Baseline adverse events to document pre-existing toxicity from prior treatment (assessed using CTCAE v4.03)
- Tumor response to platinum based chemotherapy, evaluation by CT or MRI (as defined by investigator assessment)
- Physical examination including the assessment of height, weight, pulse rate and blood pressure and BMI.
- Eastern Cooperative Oncology Group (ECOG) performance status
- Blood tests^b
 - Full blood count (CBC with differential)
 - U&E: serum creatinine (SCr), urea, K+, Na+, glomerular filtration rate assessment
 - Liver function test: Bilirubin, ALP, AST/ALT, albumin
- Radiological investigations
 - CT or MRI scan to assess disease (thorax, abdomen and pelvis)
- Other tests
 - Pregnancy tests

See Appendix G for additional requirements for Korean sites only.

Where laboratory investigations have not been performed within the 7-day period prior to starting treatment, they must be repeated on day 1 of cycle 1.

4.1.3 Baseline documentation of “target” and “non-target” lesions

All measurable lesions (nodal and non-nodal) up to a maximum of five lesions in total (and a maximum of 2 lesions per organ), representative of all involved organs, should be identified as **target lesions** and recorded and measured at baseline. Target lesions must be 10 mm in the longest diameter to qualify, or 15 mm in the short diameter for lymph nodes. Target lesions should be selected on the basis of their size (lesions with the longest diameter) and their suitability for accurate repeated measurements (either by imaging techniques or clinical assessments).

A sum of the longest diameter (LD) for *all target lesions* will be calculated and reported as the baseline sum LD. The baseline sum LD will be used as the reference by which to characterize the objective tumor response.

All other lesions (or sites of disease) should be identified as **non-target lesions** and should also be recorded at baseline. Measurements of these lesions are not required, but the presence or absence of each should be noted throughout follow-up.

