4.8.1 Efficacy outcome measures

Only response evaluation per RECIST will be entered into eCRF for the Extension period.

The primary efficacy outcome measure is as follows:

PFS, defined as the time from randomization to the first occurrence of disease progression (as determined using RECIST v1.1 criteria and assessed by the Investigator) or death from any cause on study. Death on study is defined as death from any cause within 30 days of the last dose of study treatment regimen. Tumor progression will be assessed locally at each site by the investigators according to RECIST 1.1. No independent review of tumor progression is planned. PFS with disease progression determined by iRECIST will also be examined in exploratory data analysis for the combination arm. The secondary efficacy outcome measures in all subjects are as follows:

- OS (overall survival) defined as the time from randomization until death from any cause.

- ORR (overall response rate) defined as the subjects achieving Complete Response or Partial Response as defined by RECIST 1.1.
- CBR (clinical benefit rate) defined as subjects achieving Complete Response, Partial Response or Stable disease \geq 24 weeks

Methods of measurement

The following definitions and criteria (from RECIST 1.1) should be used for the baseline evaluations of existing disease and for the ongoing evaluation of tumor responses. All measurements should be taken and recorded in metric notation, using a ruler or callipers. In the case of skin lesions, documentation by color photography and a measurement with a ruler to estimate the size of the lesion is recommended.

- **Measurable disease** - the presence of at least one measurable lesion.
- **Measurable lesions** – non-lymph node lesions that can be accurately measured in at least one dimension with LD 20 mm using conventional techniques or 10 mm with spiral CT scan, or 15mm for lymph nodes with spiral CT.
- **Non-measurable lesions** - all other lesions ie, bone lesions, ascites, pleural/pericardial effusion, including lesions that do not meet the measureable criteria above.
- Conventional CT should be performed with cuts of 10 mm or less in slice thickness contiguously. Spiral CT should be performed using a 5-mm contiguous reconstruction algorithm.

All imaging methods should be performed according to institutional standards with each subject having consistency of methods beginning from baseline through the course of the study.

Table 9: Response criteria

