Evaluation of target lesions	
Complete Response (CR):	Disappearance of all target lesions
Partial Response (PR):	At least 30% decrease in the sum of the LD of target lesions, taking as reference the baseline sum LD
Progressive Disease (PD):	At least a 20% increase in the sum of the LD of target lesions, taking as reference the nadir (smallest sum) LD recorded since the treatment started or the appearance of one or more new lesions
Stable Disease (SD)	Neither sufficient shrinkage to qualify for PR nor sufficient increase to qualify for PD, taking as reference the smallest sum LD since the treatment started
Evaluation of non-target lesions	
Complete Response (CR):	Disappearance of all target lesions
Stable Disease (SD)	Persistence of one or more non-target lesion(s)

Progressive Disease (PD):	Appearance of one or more new lesions and/or unequivocal progression of existing non-target lesions
---------------------------	---

Evaluation of Best Overall Response

The best overall response is the best response recorded from the start of the treatment until disease progression and is determined as per Table 10 below.

Table 10: Definition of best overall response as per RECIST criteria

Target lesions	Non-Target lesions	Evaluation of New lesions	Overall response
CR	CR	No	CR
CR	SD	No	PR
PR	Non-PD	No	PR
SD	Non-PD	No	SD
PD	Any	Yes or No	PD
Any	PD	Yes or No	PD
Any	Any	Yes	PD

To be considered a response, CR or PR must persist for a minimum of 4 weeks. If, at the time of tumor response evaluation, either a PR or CR is observed, the same radiographic study should be repeated 4 weeks later for confirmation of response. After this confirmatory study, subjects should return to the schedule of evaluations as previously described.

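### Table 9 defines non-target CR by the target lesions, and nodal targets qualify on short diameter but are summed on longest, so some response and progression calls are contradictory or depend on the axis used

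*Combined protocol and SAP*

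**What the plan says.** **Entry as a target.** Section 4.1.3 takes as targets "All measurable lesions (nodal and non-nodal) up to a maximum of five lesions in total", with the size rule "Target lesions must be 10 mm in the longest diameter to qualify, or 15 mm in the short diameter for lymph nodes". Section 3.9 agrees on the nodal axis: "Lymph nodes must be 15mm or greater (by spiral CT) in the shortest diameter to be considered measurable". Section 4.8.1 repeats the threshold as "or 15mm for lymph nodes with spiral CT", without naming an axis.

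**What is summed.** Section 4.1.3 continues: "A sum of the longest diameter (LD) for *all target lesions* will be calculated and reported as the baseline sum LD". That sum is the reference for response. Table 9 sets PR at a 30% fall from baseline and PD at a 20% rise from the nadir, both on the longest-diameter sum. No exception for nodes appears in 3.9, 4.1.3 or 4.8.1.

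**Complete response.** Table 9 defines target CR as "Disappearance of all target lesions". The same four-column logic in Table 10 also needs a non-target status, but under the non-target heading Table 9 prints the identical words for CR. Non-target SD is persistence of at least one non-target lesion.

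**Setting.** Sections 3.9 and 4.8.1 instruct assessors to use these printed criteria, described as coming from RECIST 1.1. Assessment is local, with no independent review planned (3.8, 4.8.1). Section 4.1.5 does not require measurable disease for entry.

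**The concern.** Three defects sit in the rules that turn scans into endpoints.

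- **(a)** Non-target CR is decided by the wrong set of lesions.
- **(b)** A node is admitted on one axis and then followed on another.
- **(c)** Nothing says at what size a node that is still visible counts as resolved.

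ORR and CBR are secondary endpoints in each arm (section 2.2). PD on the diameter sum is one route to a primary PFS event (section 3.8). Five institutions in three countries assess locally (section 4.1.4). If some apply the printed text and others apply the named standard, the documents describe no step that would detect the difference.

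**Working it through.** There is no stated figure to reproduce. The check applies Tables 9 and 10 literally, then applies the protocol's own thresholds to assumed node sizes.

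**(a) Non-target CR row.**

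- *All targets gone, one non-target lesion (say, in bone) persists.* Non-target CR is met, because all targets have disappeared. Non-target SD is also met, because a non-target lesion persists. Table 10 maps CR/CR to overall CR and CR/SD to overall PR, so the subject has two answers.
- *Targets remain, all non-target lesions gone.* Neither non-target CR nor non-target SD is met. Overall response is unharmed, because the PR and SD rows of Table 10 need only that non-target disease has not progressed.
- *No target lesions, which section 4.1.5 permits.* The rule refers to lesions the subject does not have, so it cannot classify response. Apart from the progression rows, every row of Table 10 needs a target status.

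**(b) Axis.** Percentage change = (follow-up - baseline) / baseline. The thresholds from Table 9 are -30% for PR and +20% for PD, with baseline taken as the nadir. The sizes below are assumptions for a subject with a single target node, given as short x long in mm.

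| Baseline to follow-up | Longest diameter (as written) | Short diameter |
|---|---|---|
| 16 x 28 to 10 x 22 | (22-28)/28 = -21.4%, SD | (10-16)/16 = -37.5%, PR |
| 16 x 20 to 14 x 14 | (14-20)/20 = -30.0%, PR | (14-16)/16 = -12.5%, SD |
| 16 x 24 to 20 x 26 | (26-24)/24 = +8.3%, SD | (20-16)/16 = +25.0%, PD |
| 18 x 22 to 18 x 27 | (27-22)/22 = +22.7%, PD | (18-18)/18 = 0%, SD |

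The category changes in both directions, for response and for progression.

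*Dilution by other targets.* Take a node going from 16 x 28 to 8 x 20 mm, plus an unchanged 40 mm non-nodal target. Longest diameters throughout: (60-68)/68 = -11.8%. Short diameter for the node only: (48-56)/56 = -14.3%. Both are SD. The effect is largest when nodes make up most of the sum.

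**(c) Nodal CR.** A visible node has not disappeared, so target CR is withheld until no node is seen. The subject is then PR or SD by the sum. ORR counts CR and PR alike, so (c) alone mainly moves CR to PR. Any loss from ORR comes through the axis in (b).

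**Weight of one subject.** If all 30 in an arm are counted, one changed responder moves ORR by 1/30 = 3.3 percentage points. Scans are 8 weeks apart (section 4.8), so a PD call shifted by one scan moves that subject's PFS by 8 x 7 / 30.4 = about 1.8 months. The design contrast is a median of 2 versus 4 months (section 7.1).

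**The case against.** The strongest reply is that the endpoints are tied to RECIST 1.1 by name throughout (sections 2.1, 2.2, 3.1, 3.8, 4.8.1 and Appendix A). On that view Table 9 is only a faulty paraphrase, and trained assessors will follow the standard. The non-target CR row is plainly a copy error, and its intended meaning can be recovered from its heading and from the SD row beside it.

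Part of this stands. It means that misclassification is conditional: it occurs if the printed rules are applied literally, or if sites differ. It does not dispose of the point, because sections 3.9 and 4.8.1 make the printed definitions the working instruction and no independent review is planned. The copy-error argument also does nothing for the nodal axis, where the wording is explicit and covers all targets.

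It is also fair to say that (a) and (c) mostly move subjects between CR and PR, leaving ORR and CBR unchanged. The exception is subjects without target lesions, whose response is undefined.

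A reader might infer that response in nodal disease is systematically under-called. The worked cases do not support that: 16 x 20 to 14 x 14 mm is over-called on longest diameter relative to short. A reader might also infer that a subject with a nodal target can never be CR. That too goes further than the text, since a node no longer seen has disappeared.

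**Conclusion.** The rules are wrong as written, through internal inconsistency. The non-target CR row gives two overall responses for one scan pattern and none for subjects without targets. The nodal axis can change PR/SD and SD/PD calls in either direction, which can affect ORR, CBR and the progression component of primary PFS. CBR changes only when SD has not lasted 24 weeks or when the call crosses into PD. The missing nodal CR rule mainly affects CR versus PR.

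The number of subjects affected cannot be derived, because the documents give neither the share with nodal targets nor node sizes. Under an assumed share of 20% to 40%, 6 to 12 of 30 per arm would have a node in the sum. A reader might take that as a count of misclassified subjects. It is not: it counts those measured on the disputed axis, and many would keep the same category, as the two-target example shows.

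The sample size of 30 per arm and its power calculation are untouched.

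**What to change.** 1. In Table 9, change non-target CR to disappearance of all **non-target** lesions. Add a line to Table 10 for subjects with no target lesions.
2. In section 4.1.3 and Table 9, state which axis a nodal target contributes to the sum and when a target node counts as CR, consistent with the RECIST 1.1 standard the protocol names. RECIST 1.1 is not in the reference list, which holds only the iRECIST guideline, so add the citation. No size limit is proposed here because the documents give none.
3. Make sections 3.9, 4.1.3 and 4.8.1 agree, including the nodal axis missing from 4.8.1, and apply one rule at all sites.
4. Where nodal targets have already been scored on a different axis, check response and progression from existing scans and report this as a sensitivity analysis.

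Steps 1 to 3 cost a wording change and site guidance. Step 4 needs no new imaging but does need some re-measurement, since in the Extension period only the RECIST evaluation is entered in the eCRF (section 4.8.1). The readers are local and may already know outcomes, which is why the result should be a sensitivity analysis and not a replacement for the original calls. Sample size and power do not change.
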